The central hypothesis motivating this study is that remote patient monitoring (RPM) of infectious disease patients can efficiently facilitate self-isolation. Additionally, RPM can assist in more rapid identification of patients at risk, facilitate detection of patient deterioration, and enable early interventions, all of which play a vital role in resource utilization and outcomes.

Specific Aims

Aim-I **To develop and test a clinical care pathway that can be utilized in similar epidemic conditions in the future**. To study this aim, we will be using the COVID-19 medical surge as a condition to evaluate the framework of delivering care through remote patient monitoring. The success of this care delivery model will be evaluated on ease of model implementation, patient satisfaction, clinical outcomes, and the utilization of shared decision making.

Aim-II **To evaluate remote patient monitoring for appropriate resource utilization in epidemic and pandemic conditions**. To evaluate this aim, we plan to compare the emergency department (ED) visits and inpatient admission of patients with and without wearable remote patient monitoring devices. Additionally, we will compare the number of patients that required critical interventions (mechanical ventilation and ECMO) during the hospital stay.

Aim III **To evaluate the utilization of wearable technology for upfront predictions of patients that would require inpatient admissions.** To evaluate this aim, patients who are diagnosed with COVID-19 and are undergoing self-quarantine will be closely monitored using a wearable device, and sharedclinical decisions will be made based on the monitored data and patient diary. The comparison group will be patients undergoing routine standard of care at the hospital. ED visits, inpatient hospital admissions, and patient satisfaction will be the outcome measures compared between the two groups.

Aim IV To evaluate the association between early identification of critical, abnormal vital signs and the prevention of serious adverse events. To evaluate this aim, patients in the monitored group and non-monitored group will be compared for ED visits, inpatient admissions, length of hospital stay, and serious adverse events.

Objectives

The primary purpose of the study is to compare the number of inpatient admissions between the monitored and non-monitored patients.

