The secondary endpoints are to compare the number of ED visits, length of stay, patient satisfaction, the incidence of mechanical ventilation, ECMO, and serious adverse events (events requiring extended hospital stay).

Methods

In this prospective observational study, we are planning to recruit COVID-19 positive patients visiting emergency rooms (ER) associated with Montefiore Medical Center

Inclusion Criteria

- Diagnosis of COVID-19 (first-time COVID-19 diagnosis)
- Able to read and understand English

- Able to navigate and fulfill tasks on an electronic tablet
- 21 years and older
- Patients that do not require an inpatient admission as per the treating physician
- Patients who are insured through Medicare
- Patients who are staying in the same household for at least 15 days

Exclusion Criteria

- Have never used a mobile phone or tablet in the past
- Patients with an implanted pacemaker
- Patients with a diagnosis of hyperhidrosis
- Acute allergic reactions to the patches
- Confirmed diagnosis of psychiatric illness or anxiety disorder
- All private insurance patients

Recruitment Strategy

Every day around 4 pm, the research team will generate a list of patients who were tested COVID-19 positive and are discharged from ER without requiring inpatient admission. This list will include all the COVID-19 positive patients from all the emergency departments associated with Montefiore Medical Center. The potential patient list will be generated on every alternate day; for example, the list will be generated on (Monday, Wednesday, and Friday). We are only planning to enroll 5-6 patients on a single day. Alternate day enrollment will potentially allow us to have a balance in the number of patients in the intervention and the control group. Also, it helps us to streamline the study logistics. After screening for inclusion and exclusion criteria, the research team will identify potential patients eligible for the study.

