The research team will call the patients in the evening and explain the purpose of the study and will obtain oral consent. Before calling the patient, the research team will review the EPIC notes to make sure their COVID results are shared and discussed with the patients. Oral consents will serve as a method of patients giving consent for engaging in the study discussion. The paper consents will be delivered to the patients with the study materials (tablet, sensors SPO2, and blood pressure cuff). After reading the consents, patients have the opportunity to decline participation in the study and return the study materials. Once patients sign the consent, patients will have two options to return the signed copy. Either they can take a picture of the signature page and email or text it to the research team, or at the end of the study, they can return the signed consents along with the tablet. We will keep a registry of the consenting process. For patients who email the signature, the investigator portion will be signed and dated on the day of receiving the email. For patients who are returning the signed consent with the tablet package, the investigator portion will be signed and dated on the day of receiving the tablet.

Delivery and Return of the Study Materials

The following day morning, the research staff will drop off the monitoring packages at the patient's preferable drop-off locations. The research team will call the patients to confirm the receiving of the study materials. Once the packet is delivered, the study team will share the details of the patients with ImagineMic, the external company which will be monitoring the patients. Once the patient completes

the 14 days of participation, the patient is required to return the study materials to the study team. The research team will make the necessary arrangements for the return of the study materials.

External Monitoring

ImagineMic will be monitoring the patients for CDC recommended 14 days. (25) ImagineMIC has extensive monitoring experience and is providing services in different capacities and capabilities. (25) ImagineMic uses a secure, HIPPA compliant platform for monitoring the patients. Additionally, round the clock, licensed healthcare professionals continuously monitor these data from a monitoring intervention center. Detailed monitoring plans are explained in the submitted brochure (Appendix-1).

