Monitoring will be prematurely terminated if the patient requires inpatient hospitalization; in all other cases, monitoring will be continued for fourteen days. During the monitoring period, patients will have the opportunity to call and speak to the medical professional at the Monitoring Intervention Center and also can call 911 in case of a severe emergency. Additionally, submitted is the guidelines put together by IMagineMic regarding the treatment and transfer of COVID-19 patients from home to the emergency (Appendix-2)

The patients will be remotely monitored for their vital signs such as blood pressure, heart rate, SPO₂, skin temperature, respiratory rate, two lead ECG, and accelerometer.

All the collected physiologic data will be transmitted to a central monitoring station where it will be evaluated continuously by licensed healthcare workers (MD, RN, and NP) who will provide real-time support to the patients. Also, the research team will obtain all the data points for future analytic purposes. Additionally, the research team will conduct a 30 day follow up phone call to catch information needed in case subjects end up visiting an outside institution.

Control Group

In this study control group will be patients those patients who are COVID positive and discharged from the ER and are not contacted by the study team during the same study period. In order to avoid chronological bias, it is essential to have controls from the same period as in the intervention group. The standard of care, the presentation, and the outcome of the disease are very much different in the surge phase of the COVID when compared to post surge months. Hence it is crucial to avoid chronological bias when comparing intervention and control groups. Additionally, in terms of evaluating the efficacy of the intervention, using patients from the surge period as a control group could potentially impact the conclusion of the study.

Regarding the care given to the control patients, Montefiore Emergency Department has a standard of operating protocols for patients discharged from the emergency room. All the usual standard of care available for the patients discharged from the emergency room will be provided to the patients, including telephone consultations. The study team will not interfere or dictate the care provided to the control patients.

Technology

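### Controls are defined as patients not contacted, which lets patients who were called but not reached count as controls, while the monitored group holds only patients who were reached

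*Combined protocol and SAP*

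**What the plan says.** The only definition of the comparison group is in the Control Group section: COVID-positive patients "discharged from the ER and are not contacted by the study team during the same study period". The section gives avoidance of chronological bias as its reason for choosing controls from the same period.

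Recruitment Strategy describes how a patient comes to be contacted. After eligibility screening there is a chart check, in which "the research team will review the EPIC notes to make sure their COVID results are shared and discussed with the patients". Then comes the call: "The research team will call the patients in the evening and explain the purpose of the study and will obtain oral consent". Under Delivery and Return of the Study Materials, monitoring starts only after a further step: "The following day morning, the research staff will drop off the monitoring packages".

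Recruitment Strategy also says "The potential patient list will be generated on every alternate day", although the same paragraph speaks of a list made every day. It adds "We are only planning to enroll 5-6 patients on a single day" and "Alternate day enrollment will potentially allow us to have a balance in the number of patients in the intervention and the control group".

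The primary purpose, under Objectives, is to "compare the number of inpatient admissions between the monitored and non-monitored patients". Statistical Analysis names a chi-square test for categorical outcomes and describes no matching or covariate adjustment.

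**The concern.** Group membership should rest on something fixed at or before the start of follow-up. Here it rests on a recruitment event after discharge. A patient enters the monitored group only by being reachable that evening, agreeing, and receiving a package the next morning. The plan does not say what counts as contact, how many attempts are made, or where a patient goes who is selected but not reached. On a literal reading such a patient can be a control, and nothing elsewhere keeps that patient out.

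Some patients may miss the call because they have returned to the ER, been admitted, or become too ill to answer. If so, early admissions are filtered out of the monitored group and may be added to the controls. That would look like prevention of admissions, which is the study's primary claim. A random calling order or a common start date would not remove it.

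A patient held back because results have not been shared also fits the control definition. This is the lesser route: the delay is administrative, and the documents do not link it to severity.

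**Working it through.** **The plan's own figure.** Statistical Analysis gives 150 per group, 15% admission in controls, a reduction of 10% and 80% power. Read as 15% versus 5% at two-sided 0.05, the usual formula gives 141 per group, or 160 with continuity correction. Power at 150 is 82.6% by normal approximation and 78.5% with the corrected chi-square. The sample size is consistent with its inputs and is not at issue. The useful benchmark is the planned effect of 10 points.

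**Inputs for the illustration.** All are assumptions except the group size of 150, the chi-square test and the 0.05 level:
- no true effect of monitoring
- admission risk 0.10 if reachable, 0.20 if not
- fraction u of calls unanswered, 10% to 40%
- a non-call pool (for example off-day discharges) equal in size to the called pool, with the same mix of reachable and unreachable patients
- every unreached patient counted as a control, and everyone reached enrols

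**Formulas.**
- Monitored risk: M = 0.10, since all were reached.
- Non-call pool risk: N = 0.10(1 − u) + 0.20u = 0.10 + 0.10u.
- Control risk with unreached patients included: C = (N + 0.20u) / (1 + u).
- Total spurious reduction: C − M. Remainder after barring unreached patients: N − M.

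**Results.**

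| u | N | C | C − M (points) | N − M (points) | Share removed by barring |
|---|---|---|---|---|---|
| 10% | 0.110 | (0.110 + 0.020)/1.10 = 0.118 | 1.8 | 1.0 | 45% |
| 25% | 0.125 | (0.125 + 0.050)/1.25 = 0.140 | 4.0 | 2.5 | 38% |
| 40% | 0.140 | (0.140 + 0.080)/1.40 = 0.157 | 5.7 | 4.0 | 30% |

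**Effect on the test.** Summing the binomial probabilities of all tables at 150 per group in which the uncorrected chi-square gives P < 0.05, the false-positive rate for C versus M is 7.9%, 18.6% and 31.4% for the three rows. For N versus M it is 5.9%, 10.5% and 18.6%. With equal risks it is 5.0%.

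**Two checks.**
- If unreached patients carry the same 0.10 risk, N = C = M and the bias is zero for every u.
- All selected patients, reached or not, have risk 0.10(1 − u) + 0.20u = N, the same as the never-selected pool. That comparison shows no difference in any row, provided selection for a call is unrelated to risk.

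**Where the bias sits.** More than half of it (55% to 70%) arises because the monitored group contains only reached patients. The control wording adds the rest.

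**The case against.** The strongest reply is that the plan nowhere sends unanswered calls to the control group. An attempted call may count as contact, and a held-back patient may simply be called later. The alternate-day sentence is compatible with controls drawn from off-days. The study schematic, not available in the text reviewed, might show the patient flow. All of this is fair: a reader might infer that an unreached patient becomes a control by rule, and the documents do not support that. What stands is that the wording permits it and nothing in the text excludes it. The alternate-day sentence speaks of balancing numbers and does not say who the controls are.

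The second reply is that excess risk among unreached patients is assumed. That is also right. There is no reach rate, no reason for non-answer and no risk figure. If the list covers same-day discharges, only hours separate discharge from the call. The mechanism is plausible, but its size is unknown.

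Third, the net direction is not certain. The 30-day call under External Monitoring is meant to catch visits to outside institutions and is described for study subjects. Controls are by definition not contacted, so their outside admissions may be missed, which would bias against monitoring. A reader might infer that the overall bias can only favour monitoring, but that holds only for the mechanism described here.

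Finally, one might picture unreached patients as a third of the controls, which at 30% risk would put the false-positive rate near 40%. With equal pools, even 40% unanswered gives only 0.40/1.40 = 29% of controls, and patients left uncalled under the daily cap would dilute it further.

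**Conclusion.** The point holds as a defect of definition with a conditional consequence. Control status depends on an undefined event after discharge, the wording admits selected but unreached patients, and the only stated test is unadjusted. If those patients have excess early risk, this mechanism produces a false benefit: about 1.8 to 5.7 points in the illustration, of which 1.0 to 4.0 remain even when they are kept out of the controls. These figures rest on the assumed 10% and 20% risks, 10% to 40% unanswered calls and equal pools. With no excess risk the bias is zero.

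The documents do not show that deteriorating patients will in fact be moved into the control group. Because the wording determines who enters the primary comparison, and a call log may not be recoverable later, it should be settled before enrolment.

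**What to change.** **Define the groups before dialling.** In Control Group, replace the contact criterion with wording such as: *Controls are eligible ER discharges, screened by the same criteria, who were never selected for a study call.* Listing day would also serve as the dividing rule, once the daily and alternate-day statements in Recruitment Strategy are reconciled.

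**Log every selected patient.** Extend the consent registry already planned under Recruitment Strategy to record each selected patient as reached, not reached, held back or declined. Bar all selected patients from the control group and show these counts in the patient flow.

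**Report the all-selected comparison prominently.** Next to monitored versus control, give admissions in all selected versus never-selected patients from chart data, under the same IRB basis as is used for the control charts. Barring alone removes only about 30% to 45% of the modelled bias, so this should not be a side analysis.

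**Cost.** One reworded sentence, a small extension of the registry and somewhat fewer available controls. The all-selected comparison is diluted by unmonitored patients. For example, if a quarter of selected patients go unmonitored at 15% risk and the rest have 5%, the selected rate is 0.75 × 5% + 0.25 × 15% = 7.5%. The contrast with 15% then falls from 10 to 7.5 points.

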The first DSMB meeting will be conducted after the completion of 50% of the enrollment. The safety of the RPM will be the only outcome discussed during the DSMB meetings. Additionally, all the adverse events associated with the RPM will be reported to the DSMB and the IRB. In the event of serious adverse events, the termination or the continuation of the study will be at the discretion of the IRB. No interim analysis will be conducted, and the efficacy of the study will not be discussed at the DSMB meetings.

Statistical Analysis

[figure not shown]
In this prospective observational study, we are evaluating the efficacy of continuous monitoring in preventing inpatient admissions. A sample size of 300 patients is targeted for enrollment; 150 in the monitoring and 150 in the non-monitoring group. The sample size calculation is based on the hypothesized reduction of 10% inpatient admission between the two groups; 15% admission in the non-monitoring group, 80% statistical power, and 20% type –II error.

All continuous variables will be summarized using the following descriptive statistics: mean, standard deviation, median, maximum, and minimum. The frequency and percentages will be reported for all categorical variables. No interim analysis will be performed. Quantitative variables will be compared using parametric or non-parametric t-test. A Chi-square test will be used for the comparison of categorical outcomes. All significance tests will be two-tailed, and values of P <0.05 will be considered statistically significant.

Risks and Benefits

Risks associated with this study are minimal. Complications from pulse oximeters and the LifeSignal Biosensor 1AX* are exceedingly rare. Complications that may occur in this study include feeling a small pinch when the monitors are placed and perhaps a small irritation to the skin. Subjects will be asked to provide personal information (PHI). All attempts will be made to keep the PHI confidential within the limits of the law. All the study documents will be kept in a locked file cabinet in the research office. Electronic files will be password protected. Informed consent will clearly state that by participating in this study, the patient's personal information will be shared with an external monitoring agency.

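### Controls are tied to the study period but not to calendar week, so nothing prevents them from entering earlier than monitored patients, and the planned unadjusted test would not correct for it

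*Combined protocol and SAP*

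**What the plan says.** The study is observational and compares inpatient admissions between "150 in the monitoring and 150 in the non-monitoring group".

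- **Control Group** gives the principle: "In order to avoid chronological bias, it is essential to have controls from the same period as in the intervention group". It explains that care, presentation and outcome differ between the surge and the months after it, and warns that surge-period controls could affect the conclusion. The working rule is only that controls are COVID-positive ER discharges whom the team does not contact within the study period. No order of selection, matching on date or week, or random draw is given.
- **Recruitment Strategy** limits monitored entry: "We are only planning to enroll 5-6 patients on a single day". It gives the purpose of the schedule as "Alternate day enrollment will potentially allow us to have a balance in the number of patients in the intervention and the control group". The same section describes the patient list first as daily and then as alternate-day, with Monday, Wednesday and Friday as the example.
- **Statistical Analysis** plans a chi-square test for categorical outcomes, with "All significance tests will be two-tailed, and values of P <0.05 will be considered statistically significant". It has no calendar-time stratum or covariate.

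**The concern.** The protocol treats chronological bias as a central threat, but its safeguard works only between periods. Within the period, the two groups are recruited by different mechanisms. Monitored entry is rationed by the daily cap and needs a call, consent and delivery of a kit. Control entry needs none of these and has no cap. Taking the first 150 uncontacted discharges would satisfy the plan as written. If admission risk drifted during accrual, the groups would then differ in average risk with no effect of monitoring, and an unadjusted test would attribute the difference to monitoring. At stake is the type I error of the primary comparison. The point concerns entry date only and would remain if both groups met identical eligibility criteria.

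**Working it through.** **1. The plan's own figure.** The plan gives no accrual duration; its only size figure is 150 per group. Its inputs are "15% admission in the non-monitoring group", "hypothesized reduction of 10% inpatient admission between the two groups" (read as 15% against 5%, because a relative 10% would need 8,525 per group), "80% statistical power" and two-sided 0.05. The pooled formula gives

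n = [1.96·√(2·0.10·0.90) + 0.842·√(0.15·0.85 + 0.05·0.95)]² / 0.10² ≈ 141 per group.

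Power at 150 per group is 82.6%. So 150 is not reproduced exactly, but the difference is on the safe side and does not bear on this point.

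**2. Monitored accrual time.** T = 150 / (patients per list day × list days per week).

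- Monday/Wednesday/Friday: 150/(6×3) = 8.3 weeks to 150/(5×3) = 10.0 weeks.
- Strict alternate days (3.5 per week): 150/(6×3.5) = 7.1 to 150/(5×3.5) = 8.6 weeks.
- Daily: 150/(6×7) = 3.6 to 150/(5×7) = 4.3 weeks.

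**3. Flow needed to fill controls early.** The documents give no ED flow, so this shows what would be required. Filling 150 controls in C weeks needs 150/C uncontacted patients per week, on top of the 15-21 enrolled per week on alternate days.

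- C = 2: (75 + 15 to 21)/7 = about 13-14 qualifying discharges per day.
- C = 3: (50 + 15 to 21)/7 = about 9-10 per day.
- C = 4: (37.5 + 15 to 21)/7 = about 7.5-8.4 per day.

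At the minimum flow that just fills the cap (5-6 per day), all list-day patients are enrolled. On Monday/Wednesday/Friday, the four other days supply 20-24 controls per week, so controls take 150/24 = 6.25 to 150/20 = 7.5 weeks, against 8.3-10 for monitored patients (C/T = 0.75). On strict alternate days the two times are equal.

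**4. Spurious difference with no true effect.** Assumptions: admission risk falls linearly by D points from 15% over T weeks, monitored patients are spread evenly over T, and controls are spread evenly over the first C weeks. Mean risk is then 15 − D/2 for monitored patients and 15 − D·C/(2T) for controls, so

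spurious benefit = D(1 − C/T)/2.

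Example: D = 10, T = 10, C = 2 gives 14.0% in controls against 10.0% in monitored patients, or 4.0 points. Rejection rates below are from exact binomial enumeration of the two-sided uncorrected chi-square test at 150 per group.

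| T (weeks) | C (weeks) | Fall 15% to 10%: points; false-positive rate | Fall 15% to 5%: points; false-positive rate |
|---|---|---|---|
| 7.1 | 2 | 1.8; 7.3% | 3.6; 16.1% |
| 7.1 | 4 | 1.1; 5.9% | 2.2; 9.3% |
| 10 | 2 | 2.0; 7.9% | 4.0; 18.6% |
| 10 | 4 | 1.5; 6.6% | 3.0; 12.8% |
| either | C = T | 0; 5.0% | 0; 5.0% |

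With no trend the difference is zero and the rate is 4.9%. At the minimum-flow ratio C/T = 0.75, the two falls give 5 × 0.25/2 = 0.6 points and 10 × 0.25/2 = 1.25 points. A rising risk reverses the sign.

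**The case against.** The strongest reply is that Recruitment Strategy already implies parallel accrual. Saying that alternate-day enrolment helps to balance group sizes makes most sense if controls come in alongside monitored patients, perhaps on the days between. That reading is reasonable and may be what the sponsor intends. But the sentence promises only a possible balance in numbers, and no section assigns controls to particular days or weeks.

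A second reply is that early filling may not be feasible. This stands in part. If controls had to meet the study's eligibility criteria (Medicare cover, English reading, tablet use), the pool would shrink, and at minimum flow the two groups accrue nearly or exactly together.

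A third is that the protocol contrasts the surge with later months and gives no evidence of a steep trend within 7 to 10 weeks. That also stands: the trend used here is an assumption.

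A reader might infer more: that controls will in fact be filled in the opening weeks, and that the epidemic could mimic most of the planned 10-point effect. For instance, a fall from 25% to 5% with a 2-week fill in a 10-week study gives 20 × 0.8/2 = 8.0 points and a false-positive rate of about 43%. The documents do not support that reading. It combines a control flow they never state with a fivefold fall in risk they never describe, and it relies on the alternate-day reading of a section that also says daily.

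**Conclusion.** The point holds as a gap in the design: a safeguard the protocol calls essential is stated too coarsely to do its job, and the planned analysis cannot make up for it. The accrual time of about 7 to 10 weeks follows from the protocol's own figures on the alternate-day reading; on the daily reading it is 3.6 to 4.3 weeks and there is less room for mismatch.

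The size is conditional. With early filling over 2-4 weeks and an assumed fall to 10% or 5%, the artefact is about 1-4 points against a planned 10, so the main harm is a false-positive rate of about 6-19% in place of 5%. It vanishes with parallel accrual or a flat risk. Confidence is high that the rule is missing and limited as to how large the resulting bias would be. Because the remedy is cheap, the change should be made.

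**What to change.** - **Control Group:** replace the study-period rule with sampling linked to calendar week. For each monitored patient, draw at random one eligible, uncontacted COVID-positive ER discharge from the same calendar week, for example from the nearest non-enrolment day. Use the adjacent week if too few are available.
- **Statistical Analysis:** stratify or adjust the primary comparison by calendar week or block, for example with a Cochran-Mantel-Haenszel test. Adjustment alone is not enough: if all controls came from the first weeks, later weeks would contain monitored patients with no one to compare them with.
- **Recruitment Strategy:** reconcile the daily and alternate-day statements, and say that the discharge list is also generated on non-enrolment days, since the control draw depends on it.

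With controls drawn in step with enrolment, the expected spurious difference is zero and the type I error is 4.7-5.0% in every trend scenario run. The cost is a weekly random draw, slightly more analysis work and, in thin weeks, use of a neighbouring week. The target of 150 per group does not change.

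### Consented, monitored patients are compared with never-contacted ER discharges by an unadjusted chi-square test, so any baseline difference in admission risk enters the efficacy result

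*Combined protocol and SAP*

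**What the plan says.** All references are to the combined protocol and SAP.

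- **Aim.** Objectives: "The primary purpose of the study is to compare the number of inpatient admissions between the monitored and non-monitored patients". Statistical Analysis: "In this prospective observational study, we are evaluating the efficacy of continuous monitoring in preventing inpatient admissions".
- **Monitored patients.** Recruitment Strategy: "After screening for inclusion and exclusion criteria, the research team will identify potential patients eligible for the study". Five to six are enrolled on a listing day. They are phoned, consent orally, and then receive the kit with a paper consent form. At that stage they can still withdraw: "After reading the consents, patients have the opportunity to decline participation in the study and return the study materials".
- **Controls.** The Control Group section defines them as patients "who are COVID positive and discharged from the ER and are not contacted by the study team during the same study period". It gives no sampling rule and no matching, and it does not say whether the Inclusion and Exclusion Criteria apply to them. The reason given for this choice is calendar time: "In order to avoid chronological bias, it is essential to have controls from the same period as in the intervention group".
- **Alternate days.** Recruitment Strategy: "Alternate day enrollment will potentially allow us to have a balance in the number of patients in the intervention and the control group". The other reason given is logistics.
- **Analysis.** Statistical Analysis: "A Chi-square test will be used for the comparison of categorical outcomes". Tests are two-sided at 0.05. Descriptive summaries are planned, but there is no regression, weighting, stratification or covariate list, and no rule for handling an imbalance.

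The plan does not label the chi-square as the primary test. That is inferred: admission is the primary objective, it is sized as a percentage, and no other stated test fits it.

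**The concern.** Patients enter the two groups by different routes. The monitored group is what remains after screening, a daily cap, a phone call and two chances to decline. Controls are defined by not having been contacted. Tablet ability, English reading, insurance type and willingness to take part may all go with admission risk. Both groups are ER discharges, which narrows the spread of risk but does not equalise it. The background itself says that presentations vary widely and that no valid risk-stratification tool exists.

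Concurrent controls deal with calendar time, and alternate-day lists are justified by equal numbers. Neither secures equal baseline risk. An unadjusted test credits any remaining difference to monitoring, so the study could show a benefit that does not exist or miss one that does. Enrolling more patients would not remove the bias.

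**Working it through.** **Inputs from Statistical Analysis:** 150 per group, 15% admission in controls, a reduction of 10% (read as absolute, so 5% when monitored), 80% power, two-sided 0.05. **Assumed:** every imbalance value below, because the documents give none.

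**1. The plan's own sample size.** With pooled variance under the null,

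n = [1.96·√(2·0.10·0.90) + 0.842·√(0.15·0.85 + 0.05·0.95)]² / 0.10² = 1.1836² / 0.01 ≈ 140.1, so 141 per group.

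The planned 150 is not reproduced exactly, but it exceeds 141 and gives 82.6% power by the same approximation. By exact binomial enumeration of the uncorrected Pearson chi-square, power is 84.3% and the rejection rate with no effect and no imbalance is 4.9%. Sample size is therefore not the problem here.

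**2. How imbalance enters.** Take one binary risk marker with relative risk RR, present in a fraction f_c of controls and f_m of monitored patients. With control risk fixed at 15%, the monitored group's risk without any monitoring effect is

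p_m = 0.15 × [1 + f_m(RR − 1)] / [1 + f_c(RR − 1)].

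The bias in the risk difference is p_m − 0.15.

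**3. No true effect: rejection rate of the planned test (exact).**

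| Assumed marker | Controls vs monitored | p_m | Bias (points) | Rejection |
|---|---|---|---|---|
| RR 2 | 30% vs 20% | 13.8% | −1.2 | 5.8% |
| RR 3 | 30% vs 20% | 13.1% | −1.9 | 7.4% |
| RR 2 | 40% vs 20% | 12.9% | −2.1 | 8.2% |
| RR 3 | 40% vs 20% | 11.7% | −3.3 | 13.4% |
| RR 4 | 50% vs 20% | 9.6% | −5.4 | 29.6% |

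For example, the fourth row is 0.15 × 1.4/1.8 = 0.1167. Stated directly as the monitored group's own baseline risk: 13% gives 7.8%, 12% gives 11.7% and 10% gives 25.7%. A baseline of 7.5%, half the control risk, gives 54.6%; that is an extreme case, beyond every row of the table.

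**4. Opposite direction, with a true two-thirds reduction.** Here the monitored group carries more of the marker, and its risk is p_m/3.

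- RR 2, 20% of controls vs 40% of monitored: 17.5%/3 = 5.8%, power 75.6%.
- RR 3, 20% vs 40%: 19.3%/3 = 6.4%, power 68.4%.
- RR 4, 20% vs 50%: 23.4%/3 = 7.8%, power 50.5%.

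Without imbalance, power is 84.3%.

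**5. What adjustment recovers.** Simulation with 4,000 replicates, no true effect. Overlap weighting used a logistic propensity score on the marker and four irrelevant covariates, with a sandwich standard error that allows for estimation of the score.

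| Scenario | Crude | Weighted |
|---|---|---|
| RR 2, 40% vs 20% | 7.9% | 5.0% |
| RR 3, 40% vs 20% | 13.0% | 5.2% |
| RR 4, 50% vs 20% | 29.9% | 5.6% |
| Two markers, RR 2 each, 50% vs 25%, both measured | 22.2% | 5.8% |
| The same two markers, only one measured | 21.4% | 9.8% |

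A separate simulation (40,000 runs; RR 2 to 4; marker in 50% of controls and 40% to 20% of monitored patients) gave 4.9% to 5.2% with a Cochran-Mantel-Haenszel test, against 5.5% to 29.6% crude. The gain comes from adjusting for a measured confounder and is not peculiar to one method.

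**6. Precision cost.** If the covariates explain a share R² of group membership, the effective size is about 150(1 − R²). For 15% vs 5%, power is 82.6% at R² = 0, 80.7% at 0.05, 78.5% at 0.10 and 73.6% at 0.20.

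**The case against.** The strongest reply has four parts.

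- **Eligibility.** The criteria are headed as those of the study, and the enrolment target of 300 includes the non-monitored group, so controls may be meant to meet them. The schematic, which could not be read here, might show how controls enter. This stands as far as it goes: the text is silent, and common criteria are not excluded. Phone contact and consent would still separate the groups.
- **Alternate days.** If controls came only from days without a list, group would depend partly on the day of discharge. The text does not say so, since controls are defined by non-contact. Even then, consenters from list days would be compared with everyone from the other days.
- **Size.** Every imbalance is assumed, and the mild cases cost little: 1.2 to 2.1 points of bias against a planned effect of 10. This is fair. What is certain is that adjustment is missing; how far the result would be distorted is not known.
- **Remedy.** Willingness to consent and tablet ability are not measured in controls, so a propensity score cannot remove them. Overlap weighting is also one choice among several. Both points stand. They limit what adjustment can achieve, but they do not support the crude test.

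The plan does call itself observational. It nevertheless frames the comparison as efficacy, and it gives no step that would act on an imbalance.

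**Conclusion.** The concern holds and should be settled before the data are analysed. The primary comparison is non-randomised and selected by consent, and the only test that fits it is unadjusted. Under the assumed single-marker imbalances, the false-positive rate runs from 5.8% to 29.6% instead of about 5%, with bias of 1.2 to 5.4 points. In the reverse direction, power falls from 84% to between 76% and 51%. These figures rest on 150 per group, 15% control risk and the assumed marker prevalences and relative risks; the documents fix neither the size nor the direction of any real difference. The missing adjustment does not depend on those assumptions. If adjustment is not specified in advance, any later adjustment would be chosen with the results in view.

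**What to change.** Name one adjusted primary analysis. Possible SAP wording:

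> The primary analysis compares any inpatient admission between monitored and non-monitored patients by propensity-score overlap weighting. The propensity score is a logistic model for group membership on age, sex, comorbidity (yes/no), oxygen saturation at the index ED visit and calendar period. The weighted risk difference is reported with a robust 95% CI that allows for estimation of the score, with standardised differences before and after weighting.

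Another pre-specified adjusted method would also serve; the essential step is to fix the method and covariates in advance. In addition:

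- apply the Inclusion and Exclusion Criteria to controls as far as the record allows;
- state how patients who decline after delivery of the kit are counted;
- keep the chi-square as an unadjusted supporting result;
- write association in place of efficacy in the conclusion, and state that willingness to consent and tablet ability are unmeasured in controls, so residual confounding remains.

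**Cost.** SAP wording, plus chart abstraction of five index-visit variables for 300 patients; the documents do not say that these are already captured. Power may fall below the planned 80% (step 6), and the estimate then applies to the overlap population. Only about 30 admissions are expected (150 × 0.15 + 150 × 0.05 = 22.5 + 7.5), which would limit an outcome regression. The propensity model is fitted to 150 vs 150 patients, so it is less constrained.
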